15.3. Secondary outcomes and additional analyses

Analyses for between group differences in GWG and infant weights will be assessed using the same mixed-effects modeling approach with separate models similar to the main model described above. Between group differences in binary outcomes of diet, physical activity, breastfeeding and women's wellness outcomes (depression, sleep, stress, social support) will be described between H42-HV intervention and Control arms using standard cut points for the

scales and modeled using logistic regression model based longitudinal models implemented through generalized estimation equations (GEE) approach employing group indicator, visit indicators, group by visit interaction terms and adjusting for the variable used to stratified the randomization. Robust variance estimate will be used for statistical inferences to derive 95% confidence intervals for the population-average based estimates and corresponding p-values. Conforming to recommended maternal postpartum care utilization and well-baby care utilization over time will separately be modelled using similar GEE approach as described above for the longitudinal binary outcomes.

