Obesity prevention efforts need to re-focus on women of reproductive age with greatest risk of disparities. Significant weight gain of ≥ 20 kg through adulthood is associated with a 2-fold increased risk of hypertension and cardiovascular disease (CVD) and 30% greater overall mortality²⁵. 23% of women (vs. 13% of men) gain ≥ 20 kg from age 18 to 55 years and weight gain in young adulthood is highest for Black women who gain >1 kg/year^{26,27}, often due to PPWR. To address the obesity epidemic, there is an urgent need for obesity prevention efforts to target high risk women of reproductive age, especially during pregnancy and the postpartum period^{25, 27,28}. Because pregnant women are motivated to have a healthy baby, pregnancy provides the ideal “teachable moment” to not only reduce adverse pregnancy outcomes (e.g., hypertensive disorders of pregnancy and gestational diabetes), but ultimately prevent CMD in women and their infants^{29,5} since rapid infant weight gain disproportionately affects low-income and ethnic minority groups and may explain disparities in childhood obesity³⁰⁻³⁴.

The postpartum period provides ideal opportunity to improve care transitions, sustain healthy behaviors to reduce CMD. In addition to pregnancy serving as a window to women’s future CV health, the postpartum period represents a vulnerable time for many women, particularly for socially disadvantaged women and those with a history of pregnancy complications^{35,36}. In fact, the American College of Obstetricians and Gynecologists suggested a re-design of postpartum care to reduce severe maternal morbidity and mortality, including counseling around postpartum weight loss, blood pressure monitoring and smoothing the transition into primary care³⁷. Our own research has shown gaps in postpartum care— women with recent preeclampsia and GDM have low primary care follow-up rates in the one year after delivery, regardless of insurance type, and tend to rely on the emergency room for care^{38,39}. Notably, few programs exist that target the postpartum time period to promote women’s self-care, diet, and exercise to reduce PPWR and ultimately decrease obesity and CMD risk³⁷. To reduce long-term CMD risk in women, it is crucial to extend behavioral interventions beyond pregnancy and into the postpartum period for women at highest risk for future CMD.

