9. DATA COLLECTION AND MEASUREMENTS

9.1. Overview of measures, instrument and data sources

Table 3 summarizes the measures (with references to the standard instruments) we will use and the timing of data collection aimed at minimizing participant burden. Data will be collected using 4 methods: online surveys, home scale, medical record review, and Medicaid claims data.

Measures and Instruments	Data source(s)	Timing				
		BL	36-38wk	2 mo	4 mo	6 mo
Demographics, preferred language, acculturation, & medical history ^{58,59}	Online (+ phone assisted) surveys	x				
Discrimination experiences ⁶⁰	Online (+ phone assisted) surveys	x				
Postpartum weight retention (PPWR)	Pre-pregnancy height & weight (prior to 15 wks) from medical records	x				
Gestational weight gain (GWG)	37-weeks & postpartum weights from home scale		x	x	x	x
Safety net services & home visiting care utilization and experiences	Online (+ phone assisted) surveys	x	x	x	x	x
Maternal health care utilization	Claims + Online (+ phone assisted) surveys		x	x	x	x
Health behaviors (diet ^{61,62} ; physical activity ⁶³ ; alcohol, marijuana, tobacco use ⁵⁸ ; breastfeeding ⁶⁴)	Online (+ phone assisted) surveys	x	x	x	x	x
Maternal wellness (depression ⁶⁵ , stress ⁶⁶ , sleep ⁶⁷ , social supports ⁶⁸)	Online (+ phone assisted) surveys	x	x	x	x	x
Infant weight and length (birth weight and 2, 4, and 6 months weights)	Online (+ phone assisted) surveys & medical records			x	x	x
Infant health care utilization	Claims + Online (+ phone assisted) surveys			x	x	x

Abbreviations: BL=baseline; mo=months postpartum; wk=weeks gestation.

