14.3 Infant secondary outcomes

Infant growth outcomes of weight, length, and head circumference – at birth, 4 and 6 months – will be self-reported in surveys and will be verified using infant medical records.

14.4. Other outcomes including diet, physical activity, depression, stress, sleep and social support will be self-reported using online surveys created from standard survey instruments^{85,86,87,57,80,81,72}

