15. DATA ANALYSIS

15.1 General Approaches

Compare the effectiveness of the H42-HV program using a remotely-delivered health coaching intervention integrated into home visiting with mHIP-HV among 400 pregnant and postpartum women enrolled from early home visiting programs in Maryland:

- Primary outcome: PPWR at 6 months after delivery
- Maternal secondary outcomes: GWG (37 week minus baseline pregnancy [≤ 15 week gestation] weight); Proportion with excessive GWG.
- Infant secondary outcomes: Weight at birth, 2 months, 4 months, and 6 months of age will be gathered as maternal self-report via online surveys and verified with infant medical records.
- Maternal and infant health care utilization, including receipt of postpartum care, ER visits and routine well infant visits, captured for those participants who are Medicaid recipients using claims data.
- Other outcomes: Maternal health behaviors (diet, physical activity, and breastfeeding); Maternal wellness (depression, sleep, and stress)

The main analyses for the primary and secondary outcomes will follow the ITT principle. The analysis for PPWR will utilize a mixed effects model to assess between group difference in mean of total PPWR.

15.2. Main analytic model for the primary outcome of PPWR (difference between pre-pregnancy weight and weight at 6 months postpartum).

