We will carry out the main analysis to assess the between group difference using a mixed effects model characterized by a mean model relating the outcome to the predictors and a variance-covariance model addressing variance of all available longitudinal weight outcomes and correlation between outcomes measured overtime within individual. The predictors in the mean model will include a group indicator (0 for Group B and 1 for Group A), 3 visit indicators for 2, 4, and 6 months respectively, with 0 for baseline and 1 for the specific month postpartum the visit indicator corresponding to, and the group by visit interaction terms, adjusting for study sites, BMI category, and gestation at the time of enrollment used for randomization stratification, all as fixed effects. The regression coefficient of the group by 6-months postpartum weight interaction term will estimate the primary outcome, i.e., mean difference in PPWR at 6-months between intervention and control groups. We will use an unstructured variance-covariance model to allow full flexibility on outcome variances and correlations. Data from all participants randomized will be used in this analysis, including missing data which will be included using a software specified missing indicator.

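### Infant growth is analysed only as raw weight at nominal visits, without infant sex, actual age at weighing or the collected length, so the comparison is somewhat less precise and harder to interpret than it need be

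*Combined protocol and SAP*

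**What the plan says.** The aims (Section 2) name infant growth as an infant secondary outcome. The background (Section 3) gives the reason for interest in infants: "rapid infant weight gain disproportionately affects low-income and ethnic minority groups". Three later places describe the measures, and they differ:

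- Section 14.3 defines the outcome as "Infant growth outcomes of weight, length, and head circumference – at birth, 4 and 6 months", reported by the mother and verified in infant records.
- Table 3 (Section 9.1) lists "Infant weight and length (birth weight and 2, 4, and 6 months weights"), with collection at 2, 4 and 6 months and no head circumference.
- Section 15.1 keeps weight alone: "Infant secondary outcomes: Weight at birth, 2 months, 4 months, and 6 months of age will be gathered as maternal self-report", again verified in infant records.

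For the analysis, Section 15.3 says: "Analyses for between group differences in GWG and infant weights will be assessed using the same mixed-effects modeling approach". The model it refers to, in Section 15.2, has a group indicator, "3 visit indicators for 2, 4, and 6 months respectively, with 0 for baseline", and group-by-visit interactions, "adjusting for study sites, BMI category, and gestation at the time of enrollment used for randomization stratification". Covariance is unstructured. No section names infant sex, date of measurement, gestational age at birth, a z-score or a rapid-gain measure for this analysis.

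**The concern.** Raw weight in early infancy depends on the infant's sex and on exact age when weighed. The weights here are maternal reports checked against records, so a weight labelled 4 months may have been taken some time before or after that age. A visit indicator absorbs the average age at each visit but not the spread around it, nor any difference between arms.

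Two things are at stake. The first is precision: variance that could be removed stays in the error term. The second is interpretation: a higher mean weight could reflect longer infants, later weighing or more weight for length. Only the last of these bears closely on the obesity pathway in the rationale. Length would help to separate them, and it is collected, but the plan does not say how it will be used.

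**Working it through.** **1. The plan's own power figure.** Section 16 takes 360 × 0.70 = 252 analysed, or 126 per arm, with two-sided alpha 0.05 and 90% power. The formula is MDD = (1.960 + 1.282) × SD × √(2/126).

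- SDs of 5.5, 7.0, 8.0 and 8.8 kg give 2.246, 2.859, 3.267 and 3.594 kg.
- With the noncentral t distribution they give 2.255, 2.870, 3.280 and 3.608 kg.
- Table 6 states 2.26, 2.87, 3.28 and 3.61 kg, so it is reproduced.

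These figures concern maternal weight retention. No infant outcome has a power statement.

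**2. Variance due to sex and age in raw 6-month weight.** None of these inputs is in the documents; all are assumptions.

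- SD within sex and age: 0.8 to 1.0 kg
- Boy-girl difference d: 0.4 to 0.6 kg, with a 50:50 split
- Weighing uniform within ±w of nominal age, w = 0.5 to 1.0 month
- Growth rate: 0.5 kg/month

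Added variance V = (d/2)² + (0.5 × w/√3)². Share of total = V/(SD² + V). Equivalent extra infants = V/SD².

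| | Low end | High end |
|---|---|---|
| d, w, SD | 0.4, 0.5, 1.0 | 0.6, 1.0, 0.8 |
| Sex term | 0.0400 | 0.0900 |
| Age term | 0.0208 | 0.0833 |
| V | 0.0608 | 0.1733 |
| Share | 0.0608/1.0608 = 5.7% | 0.1733/0.8133 = 21.3% |
| Extra infants | 6% | 0.1733/0.64 = 27% |
| Wider interval | √1.0608: 3% | √1.271: 13% |

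For scale, take an effect with 90% power after standardisation. Raw weight would have power Φ(3.2415/√1.0608 − 1.960) = 88% at the low end and Φ(3.2415/√1.271 − 1.960) = 82% at the high end.

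A wider grid in SD units (sex difference 0 to 1.0 SD, age component 0 to 0.3 SD, at least one above zero) gives variance increases of 1% to 34%. With an assumed 126 infants per arm, power falls to between 89.7% and 80.0%.

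**3. What changes if the contrast is gain from birth.** Section 15.1 lists four infant time points and the model has three visit indicators, so birth weight is the natural baseline. The 6-month interaction is then the between-arm difference in mean gain. Any sex difference present at birth drops out of it. If half of the 6-month difference were already present at birth (an assumption), the sex term would fall to a quarter. With the same SDs kept for illustration, the shares become 0.0308/1.0308 = 3.0% and 0.1058/0.7458 = 14.2%. The SD of gain is unknown; a smaller one would raise these shares.

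Randomization is complete by 34 weeks (Table 2), so birth weight follows randomization and is itself a listed outcome. The maternal baseline precedes randomization. The difference in gain and the difference in 6-month weight are therefore separate questions for infants, and the plan does not say which is meant.

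**4. Age at weighing.** If one arm were weighed 0.2 month later on average (an assumption), raw weight would show 0.2 × 0.5 = 0.1 kg with no growth effect. With 126 per arm, the standard error of a mean difference is SD × √(2/126) = 0.10 to 0.13 kg for SDs of 0.8 to 1.0 kg. The artefact would be about one standard error at most.

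**The case against.** The strongest reply is that the planned model already addresses infant weight gain. A reader might infer from the lack of z-scores that the trial cannot show anything about rapid gain. The documents do not support that: with birth weight as baseline, the interaction terms estimate the difference in mean raw gain to 2, 4 and 6 months. What is missing is an age- and sex-standardised gain, a proportion with rapid gain, and weight relative to length.

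Other parts of the reply also stand:

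- **Sex is not a source of bias.** Allocation is randomized 1:1, so sex is balanced in expectation. Its omission costs precision only, and repeated measures may recover part of that.
- **Most of the variance remains.** Even at the high end, about 79% of the variance has other sources. It would be wrong to say that sex and age dominate.
- **The timing mechanism is uncertain.** Table 4 places support for pediatric attendance with home visitors, who serve both arms, and Section 13.0 gives all of them the same training. The 0.2-month shift is only an illustration. Still, well-infant visit receipt is a listed outcome, and randomization does not protect age at weighing from a difference in attendance.
- **Head circumference is not uncollected.** Its absence from Table 3 might suggest so, but Section 14.3 provides for maternal report and record verification. The fault is a mismatch between sections.

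Section 15.3 asks only for models similar to the main one, which leaves room for more covariates, but it names none.

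**Conclusion.** The point holds as a modest, inexpensive improvement to a secondary analysis. Three facts rest on the text alone: infant growth is reduced to raw weight at nominal visits, infant sex and actual age are not used, and length has no analysis.

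The loss of precision is certain in direction whenever weight varies with sex or with age inside the visit window. Its size rests wholly on assumed inputs: about 6% to 21% of the variance of 6-month weight, or an interval some 3% to 13% wider. It is smaller to the extent that the sex difference is present at birth. Exposure to a difference in age at weighing is possible, but nothing in the documents shows that it will occur.

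A reader might also infer that a single weight-for-length score at 6 months would settle the matter. It would not, because it does not measure gain; a change from birth is needed as well. The outcome carries no stated power, and the conclusion on postpartum weight retention is unaffected.

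**What to change.** In Sections 14.3 and 15.3, define the infant analysis as follows, in the same mixed model:

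- Sex-specific weight-for-age z-scores, including change from birth, and weight-for-length z-scores.
- Scores computed from weight and length in the medical record, with actual measurement date, infant sex and gestational age at birth. Maternal report is used only where no record exists.
- A statement that birth weight is the baseline for the change contrast.

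Confirm that infant sex, birth date and measurement dates are captured; Section 9.3.1 mentions infant characteristics but does not name sex.

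Reconcile Section 14.3, Table 3 and Section 15.1 on measures and time points. Length is in the first two only, head circumference is in Section 14.3 only, and the 2-month visit is missing from Section 14.3.

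The cost is SAP wording and a few more fields from infant records that the study already plans to obtain. Some infants will lack a paired length and will contribute weight-for-age only.

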We will use a hybrid type 1 effectiveness-implementation randomized control trial to compare the effectiveness of H42-HV integrated into home visiting compared with usual home visiting services in reducing postpartum weight retention (difference between pre-pregnancy weight and weight at 6 months postpartum) among 400 pregnant and postpartum women. We will also evaluate the implementation of the intervention to enable and sustain integration into home visiting. Ultimately, we aim to prevent CMD and its intergenerational effects by promoting healthy lifestyle and postpartum weight loss and addressing disparities in CMD among Black and Latina pregnant/postpartum women at highest risk and support for healthy infant growth from the start. Our approach allows us to not only establish the effectiveness of H42-HV but also understand the factors that enable intervention implementation to inform sustainability, further the pathway from evidence translation into practice, and facilitate greater subsequent public health impact ⁸.

2. AIMS AND OUTCOMES:

We will conduct a type 1 hybrid effectiveness-implementation trial to evaluate Healthy for Two – Home Visiting (H42-HV).

Aim. Compare the effectiveness of H42-HV integrated into home visiting compared with usual home visiting services in reducing **postpartum weight retention** (PPWR; difference between pre-pregnancy weight and weight at 6 months postpartum) among 400 pregnant and postpartum women.

Primary outcome: postpartum weight retention at 6 months after delivery (difference between pre-pregnancy weight and weight at 6 months postpartum)

Main hypothesis: H42-HV integrated into Maryland home visiting programs will reduce PPWR compared to usual home visiting comparison group.

Secondary maternal outcomes: gestational weight gain, maternal health behaviors (diet, physical activity, smoking, breastfeeding); maternal wellness (depression, sleep, social support, and stress); maternal health care utilization (postpartum OBGYN visit, PCP visit by 6 months)

Secondary infant outcomes: infant growth; newborn healthcare utilization (well infant visit receipt).

In addition to establishing effectiveness, we have an implementation aim that seeks to understand the factors that enable intervention implementation [9](#); however, those outcomes and methods will be covered by a different IRB protocol.

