8.2. Description of the recruitment and screening steps

- **Step 1.** The goal with recruitment for this hybrid effectiveness-implementation trial is to emulate the referral process from home visiting to other services and programs, such as a referral to WIC services or a food pantry. We have discussed the recruitment with all home visiting partners and received feedback about alignment of the screening and recruitment process with their intake processes.

Home visiting staff will provide potentially eligible clients with study recruitment materials, which will be in one or more of the following formats: conversation, e-mail, text messaging, video or paper flyer. The recruitment materials will have information on completing an “online interest form” to share contact information. If potentially interested, home visiting staff: 1) after obtaining permission, could refer the client to Study Team, similar to the process they use for referring clients to other services; 2) assist clients with completing an online “interest form”; 3) advise clients to complete the online “interest form” on their own time.

- **Step 2:** Study staff will complete phone screening and online/phone-assisted consent via REDCap. Consent will also involve signing a medical record release form to obtain copies of their prenatal care records and providing “minimally necessary personal data” to link the participant with their medical claims (full name, date of birth and either social security number or Medicaid ID) for participants who are enrolled in Maryland Medicaid. Copies of consent forms will be e-mailed or postal mailed to participants.
- **Step 3:** Following consent, participants will complete baseline data collection involving an online or phone-assisted survey (see Table 3) and instructions for home weight measure using the study-provided scale that will be delivered to their home.
- **Step 4:** Randomization will indicate study enrollment and occur after participant meets all eligibility criteria, has completed the baseline survey and the study team has received one

valid weight from the participant's cellular enabled scale. Participants will be randomized using an online/phone-assisted protocol. As part of our ongoing trial, our study team has already designed and implemented a REDCap assisted online consent and randomization process that we will employ for this study as well.

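### Section 15.3 describes only cut-point analyses for the scored behaviour and wellness scales; these are valid, but usually less powerful than analysing the scores already collected

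*Combined protocol and SAP*

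**What the plan says.** Section 15.3 splits the non-primary outcomes into two groups.

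- **Continuous.** "Analyses for between group differences in GWG and infant weights will be assessed using the same mixed-effects modeling approach", in separate models patterned on section 15.2.
- **Binary.** Diet, physical activity, breastfeeding, depression, sleep, stress and social support are introduced as binary outcomes that "will be described between H42-HV intervention and Control arms using standard cut points for the" scales. They are modelled by logistic regression "implemented through generalized estimation equations (GEE) approach employing group indicator, visit indicators, group by visit interaction terms", with robust variance.

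Sections 9.3.5 and 9.3.6 name instruments that yield scores: a physical activity questionnaire, the Edinburgh depression scale with one question removed, the Perceived Stress Scale, a social support questionnaire and the Pittsburgh sleep index. In Table 3 (section 9.1), the health-behaviour row and the row beginning "Maternal wellness (depression" are both marked at baseline, 36-38 weeks, and 2, 4 and 6 months.

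The status of these outcomes varies by section. Section 2 lists "maternal wellness (depression, sleep, social support, and stress" among the secondary maternal outcomes. Section 14.4 uses a lower label: "Other outcomes including diet, physical activity, depression, stress, sleep and social support will be self-reported using online surveys". No section states a cut point numerically or a power target for any of these scales.

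**The concern.** Cutting a score in two discards the differences among women on the same side of the cut. If the intervention moves the whole distribution a little, a test on the proportion beyond the cut sees only part of that movement. A real change in stress, sleep, mood or diet could then be reported as no difference, although the data to detect it were collected at five time points. If a score model is added only after results are known, it will look post hoc.

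A smaller, related point concerns depression. Section 9.3.6 removes one question, while the source cited for the scale (reference 65) is titled as a 10-item scale. Section 15.3 refers to standard cut points without saying whether the depression threshold is adapted to nine items.

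**Working it through.** **Inputs.** From section 16.0: two-sided alpha 0.05, 360 x 0.70 = 252 evaluable, 126 per arm, and the SDs and detectable differences in Table 6. All of these belong to the weight outcome. The documents give no effect size, distribution, correlation or proportion beyond a cut for the scales, so those values below are assumptions.

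**Step 1. Reproduce Table 6.** MDD = (1.96 + 1.28) x SD x sqrt(2/126) gives 2.246, 2.859, 3.267 and 3.594 kg. With the t distribution it gives 2.255, 2.870, 3.280 and 3.608 kg, against the stated 2.26, 2.87, 3.28 and 3.61. The table is right. Its standardised effect is 2.26/5.5 = 0.411 SD, borrowed here as an illustrative shift.

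**Step 2. Efficiency of a cut.** For a small shift in a normal score with a fraction p beyond the cut, efficiency relative to the score is phi(z_p)^2 / [p(1-p)]:

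- p = 0.50: 0.3989^2 / 0.25 = 0.637
- p = 0.20: 0.2800^2 / 0.16 = 0.490
- p = 0.10: 0.1755^2 / 0.09 = 0.342

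These ratios do not depend on the 0.41 SD value.

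**Step 3. Power at one visit.** Score: 0.411 / sqrt(2/126) = 3.26, so power = Phi(3.26 - 1.96) = 90%. For the cut, control proportions of 0.50, 0.20 and 0.10 become 1 - Phi(z + 0.411) = 0.341, 0.105 and 0.045. Two-proportion power is 73%, 55% and 39%.

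**Step 4. Power with the same baseline handling on both sides.** With r the baseline-to-6-month correlation, the single-visit standard error of the score contrast is multiplied by sqrt(1 - r^2) when baseline is a covariate. It is multiplied by sqrt(2(1 - r)) when baseline is a visit with a free group term. The covariate figures for the cut come from simulating a logistic model with the continuous baseline score as covariate.

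| Baseline handling | Analysis | Power, r from 0.2 to 0.6 |
|---|---|---|
| Covariate | Score | 91% to 98% |
| Covariate | Cut, 50% beyond | about 75% to 83% |
| Covariate | Cut, 20% beyond | about 56% to 63% |
| Visit, free group term | Score | 73% to 95% |
| Visit, free group term | Cut, 50% beyond | 50% to 66% |
| Visit, free group term | Cut, 20% beyond | 38% to 49% |

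Simulated type I error for the 6-month contrast, with baseline as a visit, was 0.045 to 0.053 for both score and cut. The issue is lost power, not bias.

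**Step 5. Skewed scores.** Generate the score as exp(sZ), shift Z by 0.41 and use a baseline covariate. At s = 0.8 (skewness 3.7), the score has about 80% to 90% power over r = 0.2 to 0.6 against about 73% to 83% for a median cut, a gap of roughly 7 points. At skewness about 6 and r = 0.2 the two tie at about 74%. In this model a log transform restores the normal-score figures. With a free group term at baseline, skewness 3.7 and r = 0.2, the score has no advantage (50% against 50%).

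**Step 6. Depression threshold.** If item scores are non-negative, dropping an item can only lower a woman's total or leave it unchanged. An unadapted 10-item threshold applied to nine items could therefore only undercount cases.

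**The case against.** **The text says how binary outcomes will be modelled, not that scores will be ignored.** That is fair: a reader might infer that score analyses are ruled out, and the documents do not say so. But no score model is described in any section, so the gap in the plan stands.

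**Nothing is in error.** This stands in full. A longitudinal GEE on clinical cut points with robust variance is valid and easy to interpret, and the plan claims no power for these scales.

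**The loss is not universal.** This also stands. A reader might infer that any shift across the whole score favours the score analysis. Step 5 shows otherwise under extreme skew, and an effect confined to women near the cut could shrink or reverse the difference.

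**Comparing an adjusted score with an unadjusted cut inflates the gain.** Correct, which is why Step 4 treats baseline identically on both sides. A clear gap remains for normal scores.

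**The magnitudes are borrowed.** They are. The 0.41 SD shift and the 126 per arm belong to the weight outcome, and the correlations, proportions and skewness are assumed. The powers are illustrations only.

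**The depression point is conditional.** It is. A reader might infer that a 10-item threshold will be misapplied, but no cut point is given and the item removal is disclosed. It remains a request for clarification.

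**Conclusion.** The point holds in a limited form. Section 15.3 describes no analysis of the scores themselves, and for roughly normal scores its cut-point analysis gives up a material share of the available information: about 36%, 51% or 66% with 50%, 20% or 10% of women beyond the cut (one minus the Step 2 ratios). Confidence is high that the score model is missing and that power is lost under approximate normality. The actual size of the loss in this trial is unknown.

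The finding does not make the cut-point results biased or the trial underpowered for any stated objective. The primary analysis and Table 6 are untouched. It is a low-priority improvement, worth making mainly because section 2 lists these domains as secondary outcomes and their null results will be read as evidence.

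**What to change.** Amend section 15.3 before outcome data are examined by arm.

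- For each scored scale, prespecify a continuous-score longitudinal mixed model using every collected visit, including 36-38 weeks, and name it as the main analysis of that scale. Prespecify a transformation for markedly skewed scores.
- Use the baseline score as a covariate, or constrain baseline means to be equal across arms. Do not carry over the section 15.2 coding, which has "3 visit indicators for 2, 4, and 6 months respectively, with 0 for baseline" and a free group term. For a score, its variance factor 2(1 - r) exceeds 1 - r^2 by (1 - r)^2, and below r = 0.5 it is worse than ignoring baseline. Randomization is to "occur after participant meets all eligibility criteria, has completed the baseline survey" (section 8.2, Step 4), so a baseline covariate should exclude almost no one.
- Keep the cut-point GEE as supportive, and state each cut point.
- Keep naturally binary outcomes and pre-set targets binary, such as breastfeeding and the 150 min/week activity goal in Table 4.
- For depression, analyse the 9-item score. If a cut point is also reported, prespecify one justified for nine items.

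The cost is SAP wording and modest extra analysis, with no new data collection. The downside is that mean score differences are less familiar clinically than proportions, which would still be reported.
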